5.4.2 Approximate Duration of Study

We estimate at least 15 patients a year will be enrolled in this study. With further follow-up of at least 26 months from registration to assess the progression free survival, this Phase II study would be completed in 3 years. The end of the study is the last visit of the last subject or end of collection of data from the patient's electronic health record or whichever is last.

5.5 Procedures

All Procedures including, biopsy, pathology, radiology, radiation therapy, chemotherapy, surgery, adjuvant therapy, follow up and salvage therapy, would be standard of care for this study population and disease. The experimental part of the study would be this selection of resectable patients and sequencing neoadjuvant chemoradiation prior to surgery.

5.5.1 Registration:

Patient registration can occur only after evaluation for eligibility is complete, and eligibility criteria have been met. Patients must have signed and dated all applicable consents and authorization forms.

5.5.2 Imaging

Patients will undergo standard multiparametric baseline MRI imaging at presentation, following biopsy/prior to initiation of chemo radiation, at,Pre-surgery, following surgery, and as otherwise indicated for surgical or therapy planning, then every 2 months after surgery for follow up. Imaging sequences should include a minimum of 2D diffusion-weighted imaging, T2, and FLAIR, imaging as well as 3D-IR GRE T1-weighted imaging before and after intravenous administration of 0.1 ml/kg gadobutrol (Gadavist). Dynamic susceptibility contrast perfusion imaging should be performed whenever possible using an additional 0.1 ml/kg preload injection. For each patient, if possible, serial imaging should be performed on the same scanner on which the baseline scan was obtained.

5.5.3 Immunohistopathological/Molecular Confirmation

Histopathological confirmation of a glioblastoma is required eligibility criteria for the study. This would be performed with routine stereotactic or open biopsy (preferably stereotactic with minimal skin wound). This would be at a standard of care procedure.

Synoptic description should include the presence of necrosis or vascular proliferation in the setting of a malignant glioma. IDH1, MGMT promoter methylation, EGFR amplification, TP53, and ATRX status are minimum requirements in the pathological evaluation.

5.5.4 **Radiation therapy (Standard of care)**

3DCRT and IMRT are allowed. IMRT with a simultaneous integrated boost with Fixed-gantry IMRT, helical tomotherapy, or VMAT can be used. All photon treatments shall be delivered with megavoltage machines of a minimum energy of 6 MV photons. Selection of the appropriate photon energy(ies) should be based on optimizing the radiation dose distribution within the target volume and minimizing dose to non-target normal tissue. Source-to-skin distance for SSD techniques or source-to-axis distance for SAD techniques must be at least 80 cm.

Patients will be treated in a supine position and immobilized with a thermoplastic mask and headrest. Additional immobilization devices such as a bite block are permitted.

A planning CT scan will be obtained of the cranial contents and will be fused with the MRI scans.

Definition of Target Volumes and Margins:

3D Conformal or Sequential IMRT

CTV_4600: CTV to receive 46 Gy in 23 fractions

PTV_4600: PTV to receive 46 Gy in 23 fractions

CTV_6000: CTV to receive 60 Gy in 30 fractions

PTV_6000: PTV to receive 60 Gy in 30 fractions

IMRT Dose painted

CTV_5100: CTV to receive 51 Gy in 30 fractions

PTV_5100: PTV to receive 51 Gy in 30 fractions

CTV_6000: CTV to receive 60Gy in 30 fractions

PTV_6000: PTV to receive 60 Gy in 30 fractions

Margin Definitions

CTV_4600 and CTV_5100 - Either the T2 or FLAIR abnormalities on the MRI scan, inclusive of all contrast-enhancing T1 abnormality on the MRI, plus a margin of 1-2 cm, which may be reduced around natural barriers to tumor growth such as the skull, ventricles, falx, etc. If no

surrounding edema is present, CTV should include MRI enhancement plus a 2-cm margin, with reductions permitted as described above.

CTV_6000 - Contrast-enhancing T1 abnormality plus a margin of 1-2 cm. The CTV_6000 margin may be reduced around natural barriers to tumor growth such as the skull, ventricles, falx, etc.

PTV_4600, PTV_5100- In general the PTV is the CTV plus a geometric 4 mm expansion in all dimensions. PTV may extend beyond bony margins and the skin surface.

Dose Prescription:

>95% of the volume to receive at least 4600cGy (PTV_4600), 5100cGy (PTV_5100) or 6000cGy (PTV_6000) respectively. D95 of up to 95% will be allowed to meet OAR (Organs at risk dose constraints. D95 of 95-90% would a be minor violation. D95<90% is not allowed.

Treatment Planning Priorities

1. Spinal Cord
2. Brain Stem core
3. Brain Stem surface
4. Optic Chiasm PRV
5. Optic Nerve L PRV and Optic Nerve R PRV
6. PTV_4600
7. PTV_6000
8. Brain
9. Retina L and Retina R
10. Lens L and Lens R

For photon IMRT plans, patient specific QA is highly recommended. QA is performed by delivering the plan onto a phantom and measuring the dose using an ion chamber array or other 2D/3D device. Measured dose distribution will be compared to planned dose distribution using a Gamma criterion of 3% dose difference and 3mm distance to agreement. For plans with highly modulated dose distributions a 5% dose difference and 3mm distance to agreement criterion may be used. The pass rate should be at least 90% measured for the entire plan.

Daily image-guided radiation therapy (IGRT) is required for this protocol.

5.5.5 Drug therapy – Temozolomide (Standard of Care)

Refer to the package insert for detailed pharmacologic and safety information of Temozolomide

Dosing

Temozolomide During Concomitant Radiation Therapy

Protocol treatment must preferably begin on the same day as the first fraction of radiotherapy (+/- 48 hours allowed for logistic reasons). Temozolamide will be administered continuously from day 1 of radiotherapy to the last day of radiation at a daily oral dose of 75 mg/m^2 for a maximum of 49 days. The drug will be administered orally daily during radiotherapy, as best tolerated by the patient. During weekends without radiotherapy (Saturday and Sunday), the drug will be taken in the morning. The dose will be determined using actual body surface area (BSA) as calculated in square meters at the beginning of the concomitant treatment. The BSA will be calculated from the height obtained at the pretreatment visit. Capsules of temozolomide are available in 5, 20, 100, 140, 180, and 250 mg. The daily dose will be rounded to the nearest 5 mg.

Post-Radiation – Post Operative Temozolomide

The start of the first cycle will be scheduled as soon as patient recovered from surgery and surgical wound has healed, but no later than 4 to 6 weeks from surgery. After the first post surgery visit to start TMZ (Cycle 1, Month 1), all subsequent cycles (2-12) will be scheduled every 4 weeks (28 days \pm 3 days) after the first daily dose of temozolomide of the preceding cycle.

In all treatment arms, temozolomide will be administered orally once per day for 5 consecutive days (days 1-5) of a 28-day cycle, up to 12 cycles. Patients demonstrating continued benefit from the adjuvant temozolomide can continue treatment to a maximum of 12 cycles. The starting dose for the first cycle will be $150 \text{ mg/m}^2/\text{day}$, with a single dose escalation to $200 \text{ mg/m}^2/\text{day}$ in subsequent cycles if no treatment-related adverse events > grade 1 are noted.

28 days (-3/+5) days after the last day of radiotherapy.

The dose will be determined using the BSA calculated at baseline. The BSA will be re-calculated at the pretreatment visit and if a change in more than 10% in weight has occurred, the dose of temozolomide must be adjusted according to the new BSA. Capsules of temozolomide are available in 5, 20, 100, 140, 180, and 250 mg. The daily dose will be rounded to the nearest 5

mg. The exact dose administered should be recorded in the CRF. Each daily dose should be given with the least number of capsules.

Prior to each treatment cycle with temozolomide a complete blood count (CBC) will be obtained (within 72 hours prior to dosing). Patients will be suggested to fast at least 2 hours before and 1 hour after temozolomide administration. Water is allowed during the fast period. Patients will be instructed to swallow the capsules whole, in rapid succession, without chewing them. Treatment should be given at night. If vomiting occurs during the course of treatment, no re-dosing of the patient is allowed before the next scheduled dose.

Antiemetic prophylaxis with a 5-HT3 antagonist is strongly recommended and should be administered 30 to 60 minutes before temozolomide administration.

Patients will be treated with post-radiation post-operative temozolomide for 6-12 cycles unless there is evidence of tumor progression or treatment-related toxicity

Pneumocystis carinii prophylaxis is strongly recommended during the radiation phase

Hepatic toxicity including liver failure has been observed in patients enrolled in clinical studies utilizing temozolomide. In addition, liver toxicity may occur several weeks or more after initiation of treatment or after temozolomide discontinuation. For patients with significant liver dysfunction, the risks and benefits of treatment continuation should be carefully considered.

Dose Modifications

Temozolomide During Concomitant Radiation Therapy

No dose reduction will be made but delay or discontinuation of temozolomide administration will be decided weekly according to hematologic and non-hematologic adverse events (AEs), as specified below. If the administration of temozolomide must be interrupted, the radiotherapy will proceed normally. Missed doses of temozolomide will not be made up at the end of radiotherapy. The total number of days and total dose of temozolomide will be recorded. If the duration of radiotherapy exceeds 7 weeks, then concomitant treatment with temozolomide should be stopped after 49 days of temozolomide treatment. If radiotherapy must be temporarily interrupted for technical or medical reasons unrelated to the temozolomide administration, then treatment with daily temozolomide should continue. If radiotherapy must be permanently interrupted, then treatment with daily temozolomide should stop. Temozolomide can resume with the initiation of the adjuvant phase of treatment. See Table Below:

TABLE 1: Temozolomide Dosing Interruption or Discontinuation During Concomitant Radiotherapy and Temozolomide

Toxicity	TMZ Interruption*	TMZ Discontinuation
Absolute Neutrophil Count	greater than or equal to 0.5 and less than $1.5 \times 10^9/L$	less than $0.5 \times 10^9/L$
Platelet Count	greater than or equal to 10 and less than $100 \times 10^9/L$	less than $10 \times 10^9/L$
CTC Nonhematological Toxicity (except for alopecia, nausea, vomiting)	CTC Grade 2	CTC Grade 3 or 4

*Treatment with concomitant TMZ could be continued when all of the following conditions were met: absolute neutrophil count greater than or equal to $1.5 \times 10^9/L$; platelet count greater than or equal to $100 \times 10^9/L$; CTC nonhematological toxicity less than or equal to Grade 1 (except for alopecia, nausea, vomiting).

TMZ=temozolomide; CTC=Common Toxicity Criteria.

Adjuvant treatment can be resumed if hematologic adverse events resolve (platelet $> 100 \times 10^9/L$ and ANC $> 1.5 \times 10^9/L$) during the interval from the completion of chemoradiation to the time for initiation of adjuvant chemotherapy.

Cases of hepatic injury, including fatal hepatic failure, have been observed in patients enrolled in clinical studies utilizing the agent temozolomide. In addition, it was noted that liver toxicity may occur several weeks or more after initiation of treatment or after temozolomide discontinuation. For patients with significant liver function abnormalities, the risks and benefits of treatment continuation should be carefully considered. Reference TABLE 2 below.

TABLE 2: Temozolomide Dose Levels for Maintenance Treatment

Dose Level	Dose (mg/m ² /day)	Remarks
-1	100	Reduction for prior toxicity
0	150	Dose during Cycle 1
1	200	Dose during Cycles 2-6 in absence of toxicity

Post-Radiation Post-Operative (Adjuvant) Temozolomide

Dosing is based on adverse events (AEs) during the prior treatment cycle. If multiple AEs are seen, the dose administered should be based on the dose reduction required for the most severe grade of any single AE.

On day 1 of each cycle (within the prior 72 hours), ANC $\geq 1.5 \times 10^9/L$, platelet count $\geq 100 \times 10^9/L$ and all treatment-related grade 3 or 4 non-hematologic AEs (except nausea and vomiting unless the patient has failed maximal antiemetic therapy and fatigue) must have resolved (to grade ≤ 1).

If these re-treatment parameters are not met, the treatment will be delayed to a maximum of 4 consecutive weeks. If, after 4 weeks of delay, re-treatment parameters are not met: then any further adjuvant treatment with temozolomide should be stopped.

Dose escalation

If, during the first cycle, all treatment-related non-hematologic AEs observed were grade ≤ 2 (except nausea and vomiting unless the patient has failed maximal antiemetic therapy and fatigue) and with platelets $\geq 100 \times 10^9/L$ and ANC $\geq 1.5 \times 10^9/L$: then the temozolomide dose should be escalated to dose level 1 and this dose should be used as the starting dose for subsequent cycles. If treatment after cycle 1 has to be delayed because of ongoing non-hematologic AEs of grade ≥ 2 , then no escalation is possible. If the dose was not escalated at cycle 2, then the dose should not be escalated in further cycles.

Dose reductions

If any treatment-related non-hematologic AE observed was grade > 2 (except nausea and vomiting unless the patient has failed maximal antiemetic therapy and fatigue) and/or if platelets $< 50 \times 10^9/L$ and/or ANC $< 1 \times 10^9/L$, then the dose should be reduced by one dose level (by 50mg/sqm – i.e. 150-100mg/sqm). For patients who would require dose reductions to a dose level $< 100 \text{ mg/m}^2/\text{day}$, temozolomide will be stopped. Also, if any of the same non-hematologic grade 3 AE recurs (except nausea and vomiting unless the patient has failed maximal antiemetic therapy and fatigue) after reduction for that AE, then temozolomide will be stopped.

If any treatment-related non-hematologic AE observed was grade 4 (except nausea and vomiting unless the patient has failed maximal antiemetic therapy and fatigue) then adjuvant temozolomide treatment should be stopped.

Subsequent cycles (3-12): Any dose reductions of temozolomide will be determined according to (1) non-hematologic AE during the preceding treatment cycle, as well as (2) the nadir (lowest/worst) ANC and platelet counts observed. No dose escalation should be attempted. The same dose reductions as for the second cycle should be applied.

If the dose was reduced or delayed for adverse events, there will be no dose escalation.

The reason(s) for dose reduction and/or delay must be documented. Reference TABLES 2, 3 and 4 below.

TABLE 2: Temozolomide Dose Levels for Maintenance Treatment

Dose Level	Dose (mg/m ² /day)	Remarks
-1	100	Reduction for prior toxicity
0	150	Dose during Cycle 1
1	200	Dose during Cycles 2-6 in absence of toxicity

[figure not shown]
TABLE 3: Temozolomide Dose Reduction or Discontinuation During Maintenance Treatment

Toxicity	Reduce TMZ by 1 Dose Level*	Discontinue TMZ
Absolute Neutrophil Count	less than $1.0 \times 10^9/L$	See footnote [†]
Platelet Count	less than $50 \times 10^9/L$	See footnote [†]
CTC Nonhematological Toxicity (except for alopecia, nausea, vomiting)	CTC Grade 3	CTC Grade 4 [†]

*TMZ dose levels are listed in **Table 2**.

[†]TMZ is to be discontinued if dose reduction to less than 100 mg/m^2 is required or if the same Grade 3 nonhematological toxicity (except for alopecia, nausea, vomiting) recurs after dose reduction.

TMZ=temozolomide; CTC=Common Toxicity Criteria.

TABLE 4: Dosing Modification Table

5.5.7 Other therapies (Standard of Care)

Permitted Supportive Therapy

All supportive therapy for optimal medical care will be given during the study period at the discretion of the attending physician(s) within the parameters of the protocol and documented on each site's source documents as concomitant medication.

Anticonvulsants: Anticonvulsants may be used as clinically indicated. The regimen and dosing schedule at study entry and any subsequent changes in the anticonvulsant regimen and/or dosing schedule must be recorded. EIAED use does NOT change dosing of temozolomide.

Corticosteroids: Corticosteroids may be administered at the treating physician's discretion. Doses at study entry must be recorded per Appendix I. The goal is to use the lowest clinically necessary dose of corticosteroids.

Antiemetics: Prophylactic antiemetics may be administered at the treating physician's discretion.

Pneumocystis Carinii Prophylaxis:

Both corticosteroid therapy and continuous temozolomide therapy induce lymphopenia. Patients receiving any of these drugs or both concomitantly are at an increased risk for opportunistic infections.

Therefore, prophylaxis against *P. carinii* pneumonia is recommended for all patients receiving temozolomide during radiotherapy: trimethoprim-sulfamethoxazole 1 tablet 3 times per week or monthly pentamidine inhalations (300 mg via aerosol monthly) or dapsone 100 mg po each day (except in patients with G6-PD deficiency, if known). Prophylaxis is strongly recommended to continue for the duration of radiotherapy, regardless of the lymphocyte count.

In addition, daily temozolomide has been associated with selective CD4 lymphopenia (Su, Sohn, et al., 2014). Throughout chemoradiotherapy, it is strongly recommended that all patients have CD4 quantification prior to initiation of chemoradiotherapy, at 4 weeks during chemoradiotherapy, at completion of chemoradiotherapy, and in follow up per physician choice. If the CD4 is < 200 prior to or during chemoradiotherapy, then *P. carinii* prophylaxis is required. If the lymphocyte count is ≥ 500 or the CD4 is > 200 , then *P. carinii* prophylaxis is strongly recommended but not mandatory.

If G-6PD is tested positive, administer Bactrim Single Strength once daily or Bactrim Double Strength tablet 3 times weekly (Monday Wednesday Friday). Atovaquone may be used in patients with sulfa allergy.

Non-Permitted Supportive Therapy

Growth factors are not permitted to induce elevations in neutrophil count for the purposes of: (1) administration of temozolomide on the scheduled dosing interval; (2) allowing treatment with temozolomide at a higher dose; or (3) avoiding interruption of the treatment during concomitant radiotherapy.

No other investigational drugs or devices will be allowed.

Surgical procedures for tumor debulking, other types of chemotherapy, and immunotherapy or biologic therapy must not be used. Further, additional stereotactic boost radiotherapy is not allowed. All further therapy is at the treating physicians' discretion but should be recorded in the CRF.

Carmustine wafers, TTF (tumor treating fields) or any form of brachytherapy is not permitted prior to study entry or while the patient is on this study.

5.5.8 Quality of Life assessments:

Symptom Burden

Four subscales (symptom severity, symptom interference, neurologic factor, and cognitive factor score) as well as certain individual items (fatigue, neurologic factor items, and cognitive factor items) of the MDASI-BT will be analyzed. For discrete time point analyses, the change from baseline to each follow-up time point (2, 4, 6, and 12 months from the start of treatment) will be evaluated.

To assess the prognostic ability of baseline symptom severity, symptom interference, fatigue, neurologic factor items, and neurocognitive factor items on time to neurocognitive decline, the cause-specific Cox proportional hazards regression model will be used (Cox 1972).

Assessment of Quality Adjusted Survival

Quality-adjusted survival can be defined by the weighted sum of different time episodes added up to a total quality-adjusted life-year [$U = \sum \text{quality } (q_i) \text{ of health states } K \text{ times the duration } (s_i) \text{ spent in each health state}$] (Glasziou 1990):

$$U = \sum_{i=1} q_i s_i$$

We will use Glasziou's multiple health-state (Q-TwiST) models to use the repeated measures of EQ-5D-5L. Because Glasziou's method incorporates longitudinal QOL data into an analysis of quality-adjusted survival, the health stated model must be constructed on the following assumptions:

- A1) QOL is independent from treatment.
- A2) A health state is independent from previous states.
- A3) Proportionality of quality-adjusted duration and duration of the actual state of health

Assumption A1 can be checked by plotting QOL over time according to treatment, and the t-test can be used to compare the mean QOL scores of each treatment arm.

Assumption A2 can be checked by comparing the QOL for patient groups in a given health state where the groups are defined by duration of previous health state experience using a regression model. Suitable checks for assumption A3 at minimum would be a simple plot. If data does not support these assumptions, we will use a method which uses the longitudinal QOL data directly. We will use the 5-item utility score in EQ-5D-5L for the health outcomes analysis.

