5.7 Primary Endpoints

Phase II Simon Stage 1: No study related undue toxicity or progression in the first stage patients: Toxicity is defined as: progression precluding surgery, unanticipated neurological decompensation, non-completion of neoadjuvant therapy (other than protocol defined dose adjustments or discontinuation), treatment related delay of > 6 weeks to surgery, and/or major unforeseen surgical complication requiring repeat surgical intervention including other than non-life- threatening infection like meningitis/encephalitis or septicemia.

Phase II Stage 2 (Entire Cohort): Progression Free Survival: defined as MRI defined progression (increasing FLAIR, enhancement, diffusion and or perfusion) 3 months after completion of therapy (to allow for excluding pseudo progression) OR clinical progression with new or worsening neurological symptoms related to the tumor (by MRI or clinical correlation with location) and not due to non-tumor or study related symptoms.

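### Progression is scored without reference to corticosteroid dose, so a dose change can shift 7-month status in either direction; the size of the error is unknown and the remedy is cheap

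*Combined protocol and SAP*

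**What the plan says.** Section 5.7 defines progression by two routes. The imaging route is "MRI defined progression (increasing FLAIR, enhancement, diffusion and or perfusion) 3 months after completion of therapy". The joining words let a rise in FLAIR or enhancement suffice alone. The clinical route is "clinical progression with new or worsening neurological symptoms related to the tumor", supported by MRI or by clinical correlation with location, "and not due to non-tumor or study related symptoms". Neither route names corticosteroids, and sections 5.9.1 and 5.9.2 do not either.

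On use, section 5.5.7 says "Corticosteroids may be administered at the treating physician's discretion" and "The goal is to use the lowest clinically necessary dose of corticosteroids". On recording, it says "Doses at study entry must be recorded per Appendix I". For anticonvulsants, just above, it asks for more: "any subsequent changes in the anticonvulsant regimen and/or dosing schedule must be recorded". The section's opening sentence also requires supportive therapy in general to be documented in source records as concomitant medication. Table 5.6 schedules review of those medications at screening, during chemoradiation, in the adjuvant period and in follow-up.

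Section 5.9.2 turns 7-month non-progression into the decision: continue with 7 or more of 11, and reject the null rate of 0.50 with 17 or more of 25.

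**The concern.** The clinical premise, which the documents do not state, is that corticosteroids can reduce edema and enhancement and relieve mass-effect symptoms. These are signals that 5.7 reads as tumor change. A dose that is discretionary and kept as low as possible can be expected to move during the trial. Worsening that follows a reduction can then be scored as progression, and an increase can make a progressing patient look stable.

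The trial has one arm and compares against a fixed 50%, so no concurrent control shares the error. The final decision turns on one patient: 16 non-progressors of 25 fail and 17 succeed.

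**Working it through.** **Inputs from section 5.9.2.** p0 = 0.50, p1 = 0.75, n1 = 11 with stopping at 6 or fewer, n = 25 with rejection at 17 or more. A parenthesis there says more than 17; the 17-or-more rule is used here because it reproduces the stated error rates.

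**Step 1: reproduce the plan.** With non-progression probability p,

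P(reject) = Σ over x = 7 to 11 of P(Bin(11, p) = x) × P(Bin(14, p) ≥ 17 − x).

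- p = 0.50: 0.0145 + 0.0171 + 0.0106 + 0.0032 + 0.0004 = 0.0458.
- p = 0.75: 0.1276 + 0.2293 + 0.2482 + 0.1533 + 0.0421 = 0.8005.

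Both agree with the stated 0.05 limit and 80% power.

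**Step 2: add misclassification.** Let a be the share of true non-progressors scored as progressed (steroid reduction), and b the share of true progressors scored as non-progressed at 7 months (steroid increase). The apparent non-progression rate is

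q = p(1 − a) + (1 − p)b.

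The documents give neither a nor b; the values below are assumptions.

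| a | b | q if p = 0.50 | type I error | q if p = 0.75 | power |
|---|---|---|---|---|---|
| 0 | 0 | 0.500 | 0.046 | 0.7500 | 0.80 |
| 0 | 5% | 0.525 | 0.075 | 0.7625 | 0.84 |
| 0 | 10% | 0.550 | 0.115 | 0.7750 | 0.87 |
| 5% | 0 | 0.475 | 0.027 | 0.7125 | 0.67 |
| 10% | 0 | 0.450 | 0.015 | 0.6750 | 0.52 |
| 10% | 10% | 0.500 | 0.046 | 0.7000 | 0.62 |

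Equal errors cancel at p = 0.50 but not at p = 0.75, so type I error returns to its nominal value while power does not.

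**Step 3: what the existing safeguards reach.** Table 5.6 ends chemoradiation at week 7 and puts surgery at weeks 8–12. If the 3-month rule runs from the end of chemoradiation, imaging progression counts from about week 7 + 13 = 20, which is 8–12 weeks after surgery. Most of a post-operative taper would fall before that. Dose changes after that point are not covered. The non-tumor-cause exclusion belongs to the clinical route only. Neither safeguard acts on an increase that hides progression.

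**Step 4: why a confirmation rule needs backdating.** Section 5.5.2 places scans 2 months apart after surgery. Assume exponential progression with a 7-month median. The probability of progressing in months 5–7 is 2^(−5/7) − 0.5 = 0.6095 − 0.5 = 0.1095, or 22% of progressions by month 7. If a quarter of these (assumed) were confirmed only after month 7 and dated then, q = 0.5 + 0.25 × 0.1095 = 0.527 and type I error would be 0.078. Dating confirmed progression to the first scan avoids this.

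**The case against.** The strongest reply is that the plan already holds most of what is needed. A reader might infer from the entry-only sentence that later steroid doses go unrecorded. The documents do not support that: supportive therapy is documented as concomitant medication, and reviews are scheduled in the adjuvant and follow-up periods, when 7-month status is decided. What is missing is a required dose at each MRI and a rule for using it.

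A reader might also infer that the unmarked medication review at the pre-surgery visit contaminates the endpoint. It does not feed the imaging route, which counts only from 3 months after therapy. Nor can it be said that a taper after resection will be scored as progression. The 3-month rule removes much of that period from the imaging route, and an assessor may discount taper symptoms as not due to tumor. If completion of therapy is taken to include the adjuvant cycles, the imaging route starts later still and the point rests more on the clinical route.

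Finally, section 5.9.1 does not say how progression was scored in the standard-of-care figure behind the 50%. If that figure carried similar steroid error, the type I inflation would shrink or vanish.

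These points limit the size of the concern. They do not supply the missing link, because no sentence brings steroid dose into the progression call.

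**Conclusion.** The gap is certain and sits on the primary endpoint: the scoring rule, followed as written, can mix steroid change with tumor change. Its size is unknown. The figures of 0.075–0.115 for type I error and 0.67–0.52 for power each assume one error at 5–10% with the other absent, and a null rate of 0.50 free of the same error. With both errors at 10%, only power suffers (0.62).

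A reader might infer that the trial's type I error is in fact inflated. The documents do not support that, since they give no rate and no net direction. This is a worthwhile, cheap improvement to endpoint scoring, not a demonstrated failure of the design.

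**What to change.** **Section 5.5.7.** Record the corticosteroid dose at study entry and at each MRI from the post-surgery comparison scan onward, using the concomitant medication reviews already scheduled.

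**Section 5.7.** Add two scoring rules:

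- Worsening that coincides with a steroid reduction since the comparison scan is provisional and is settled by the next scheduled scan. If confirmed, progression is dated to the first scan. Seven-month status is finalised only after the settling scan.
- A stable or improved scan after a steroid increase for tumor-related neurological symptoms does not by itself establish non-progression. The patient is assessed under the existing clinical route and, if it is met, counted as progressed from the date of worsening.

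Together these give every patient a definite status in the 17-of-25 count. If status is then classified correctly, the design keeps n = 25, type I error 0.046 and power 0.80.

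**Cost.** One case report form field per MRI, and some 7-month calls finalised up to about 2 months later. No added visits or scans, and no change to how steroids are given.

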5.6 Study Time and Events Table

Study Procedure	Screening	CRT	Pre-Surgery	Surgery	Adjuvant Treatment for 12 mos. from 4 to 6 weeks after surgery	Follow-up
Study Interval	Day-1 to -21	Weeks 1-7		Weeks 8-12	Every 2 mos. (28 day cycle)	Every 3 mos. after 12 mos. timepoint
Medical history and Examination	X					X
Screening, Labs, pregnancy	X					
Informed consent	X					
Biopsy	X			X		
Temozolomide Dosing ^a	X					X
RT Planning	X					
Radiation Therapy + Temozolomide		X				
Surgery				X		
Adjuvant Temozolomide					X ^e	
MRI	X		X		X	X
Weight	X	X		X	X	X
CBC/d ^b	X	X	X	X	X	X
QOL Questionnaires (MDASI-BT)	X		X		X	X
Concomitant medication Review	X	X			X	X
Adverse events Review ^d	X	X	X	X	X	X

a Temozolomide will continue in the adjuvant setting for a total of 12 weeks

b CBC/d weekly during neoadjuvant CRT +/- 3 days, and pre-surgery

c From the time of informed consent to the end of the study, 26 months.

d. Adjuvant Temozolomide (C1) schedule no later than 4 to 6 weeks from surgery

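### Pneumocystis prophylaxis is both required and not mandatory for a patient with CD4 below 200 and lymphocytes of 500 or more, and the protocol does not say which rule governs

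*Combined protocol and SAP*

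**What the plan says.** Section 5.5.7, under Pneumocystis Carinii Prophylaxis, gives two consecutive threshold rules.

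- **Rule A.** Prophylaxis is required "If the CD4 is < 200 prior to or during chemoradiotherapy". No lymphocyte condition is attached.
- **Rule B.** "If the lymphocyte count is ≥ 500 or the CD4 is > 200", then "prophylaxis is strongly recommended but not mandatory".

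Three other statements bear on how the rules work.

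- The preceding paragraph of 5.5.7 says: "Prophylaxis is strongly recommended to continue for the duration of radiotherapy, regardless of the lymphocyte count". Section 5.5.5 says: "Pneumocystis carinii prophylaxis is strongly recommended during the radiation phase". Both are recommendations.
- CD4 testing is itself only advised: "it is strongly recommended that all patients have CD4 quantification prior to initiation of chemoradiotherapy". The same sentence adds tests at 4 weeks and at completion of chemoradiotherapy, then in follow-up as the physician chooses.
- The Study Time and Events Table (5.6) has no row for CD4, whereas its footnote on blood counts reads "CBC/d weekly during neoadjuvant CRT +/- 3 days, and pre-surgery".

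**The concern.** Rule A depends on CD4 alone. Rule B is met by either of two conditions, one of which ignores CD4. The two rules therefore overlap, and in the overlap they give opposite answers on whether prophylaxis is mandatory.

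The overlap is clinically plausible. The paragraph containing both rules says that "daily temozolomide has been associated with selective CD4 lymphopenia", which means CD4 may fall while the total lymphocyte count is relatively preserved.

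The distinction has consequences. Section 5.5.7 leaves supportive care to the attending physician within the limits that the protocol sets. A required measure removes that discretion and a non-mandatory one leaves it in place. Which rule governs decides whether omitting prophylaxis in a patient with a documented low CD4 is a protocol deviation. The same section describes patients on temozolomide, corticosteroids or both as being at raised risk of opportunistic infection.

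**Working it through.** The plan states no figure to reproduce. The check applies both rules to every combination of inputs and then looks for text that ranks them.

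**Inputs (all from 5.5.7).** Rule A applies if CD4 is measured and CD4 < 200. Rule B applies if lymphocytes ≥ 500, or if CD4 is measured and CD4 > 200. Since CD4 testing is not compulsory, 'not measured' is counted as a CD4 state. That gives 4 CD4 states × 2 lymphocyte states = 8 combinations.

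| CD4 | Lymphocytes | Rule A: required | Rule B: not mandatory | Result now | Result after the fix |
|---|---|---|---|---|---|
| < 200 | < 500 | yes | no | required | required |
| < 200 | ≥ 500 | yes | yes | **conflict** | required |
| = 200 | < 500 | no | no | neither rule | not mandatory |
| = 200 | ≥ 500 | no | yes | not mandatory | not mandatory |
| > 200 | < 500 | no | yes | not mandatory | not mandatory |
| > 200 | ≥ 500 | no | yes | not mandatory | not mandatory |
| not measured | < 500 | no | no | neither rule | neither rule; general recommendation applies |
| not measured | ≥ 500 | no | yes | not mandatory | not mandatory |

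Exactly 1 of the 8 combinations is in conflict now, and 0 of 8 after the fix. Combinations under neither rule fall from 2 to 1.

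**Is there a ranking elsewhere?** The clause about disregarding the lymphocyte count in 5.5.7 qualifies a strong recommendation, so it neither makes prophylaxis mandatory nor places Rule A above Rule B. The sentence in 5.5.5 has no thresholds. By contrast, 5.5.5 does state a precedence for adjuvant temozolomide dosing: when several adverse events occur, the most severe grade decides. No such sentence accompanies the prophylaxis rules.

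**Can the overlap occur?** CD4 cells are a subset of lymphocytes. No units are printed. Assuming both thresholds use the same unit:

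- at a lymphocyte count of 500, CD4 is below 200 whenever the CD4 share is below 200/500 = 40%;
- at 1,000, whenever it is below 200/1,000 = 20%.

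These figures illustrate that the combination is possible. They are not estimates for this population.

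**How often is each count available?** Blood counts with differential are weekly over weeks 1–7. CD4 has three advised time points before, during and at completion of chemoradiotherapy. The lymphocyte condition of Rule B will therefore be on file more often than the CD4 condition of Rule A, and the conflict arises only in patients whose CD4 is actually measured.

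**The case against.** The strongest reply is that context points to one sensible reading. Rule A is unconditional. The paragraph opens with CD4 depletion as its reason for adding a CD4 rule, so letting a total lymphocyte count override a measured low CD4 would defeat its purpose. Since CD4 testing is optional, the 'or' in Rule B may have been meant to cover whichever count is available. Most clinicians would probably follow the stricter sentence. Moreover, prophylaxis is recommended for all patients during radiotherapy, so neither reading tells anyone to go without it. Finally, 1 of 8 is a count of logical cells, which are not equally likely, and it depends on how the cells are drawn (1 of 6 if unmeasured CD4 is left out).

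Much of this stands. The practical reach is small, and the cell count describes where the contradiction lies, not how often it will occur. It would also be too strong to say that Rule B displaces Rule A: read literally, both apply. But the sensible reading is an inference that the text does not state. A rule that separates required from optional care should not depend on the reader supplying the precedence.

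**Conclusion.** The concern holds. Two adjacent safety instructions contradict each other for patients with CD4 below 200 and lymphocytes of 500 or more, and nothing in the document resolves it. The contradiction covers 1 of the 8 combinations listed, and it is the one that selective CD4 lymphopenia would produce. The documents do not give the share of patients affected. The conclusion rests only on the literal wording of the two sentences; the percentages shown additionally assume common units.

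The consequence is limited to whether prophylaxis is mandatory for these patients. Endpoints, sample size and analysis are not affected. It should be corrected because it is a contradiction in a safety rule and costs almost nothing to remove.

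**What to change.** Reword the two sentences in 5.5.7 by amendment, along these lines:

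- CD4 below 200 before or during chemoradiotherapy makes prophylaxis required, regardless of the lymphocyte count.
- Prophylaxis is strongly recommended but not compulsory if CD4 is 200 or more, or if CD4 was not measured and lymphocytes are 500 or more.

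This also assigns CD4 of exactly 200 with lymphocytes below 500, which now falls under neither rule. Patients with unmeasured CD4 and lymphocytes below 500 remain under the existing recommendation for all patients; the sponsor may wish to add a specific rule for them.

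A single clause giving the CD4 rule precedence would also remove the conflict, but would leave the CD4 = 200 gap. Replacing 'or' with 'and' in Rule B is worse. Rule B would then cover only CD4 above 200 with lymphocytes of 500 or more (1 combination) and Rule A would cover 2, leaving 8 − 3 = 5 combinations under neither rule.

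The cost is the amendment itself, plus mandatory rather than strongly recommended prophylaxis for patients in the conflicting combination, whose number the documents do not allow one to estimate.
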